## LIST OF ABBREVIATIONS

Abbreviation	Explanation
AE	Adverse Event
ANCOVA	Analysis of Covariance
BMI	Body Mass Index
CMT	Cognitive Muscular Therapy
CI	Chief Investigator
DMC	Data Monitoring Committee
DSPT	Data Security & Protection Toolkit
EDI	Equality, Diversity and Inclusion
EMG	Electromyography
EQ-5D-5L	EuroQol 5 Dimensions 5 Levels
FCP	First Contact Practitioner

GAKS	Global Assessment of Knee Symptoms
GCP	Good Clinical Practice
GP	General Practitioner
HES	Hospital Episode Statistics
HRA	Health Research Authority
IRAS	Integrated Research Application System
ISRCTN	International Standard Randomised Controlled Trial Number
ITT	Intention-To-Treat
KL	Kellgren-Lawrence (grading for OA severity)
MMSE	Mini Mental State Examination
MSK CATS	Musculoskeletal Clinical Assessment and Triage Services
NHS	National Health Service
NICE	National Institute for Health and Care Excellence
NIHR	National Institute for Health and Care Research
NJR	National Joint Registry
OA	Osteoarthritis
OARSI	Osteoarthritis Research Society International
OMERACT	Outcome Measures in Rheumatology
PCS	Pain Catastrophizing Scale
PI	Principal Investigator
PPIE	Patient and Public Involvement and Engagement
PSEQ	Pain Self-Efficacy Questionnaire
QALY	Quality-Adjusted Life Year
R&D	Research and Development
REC	Research Ethics Committee
REDCap	Research Electronic Data Capture
RfPB	Research for Patient Benefit
SAE	Serious Adverse Event
SOP	Standard Operating Procedure
TIDieR	Template for Intervention Description and Replication
TMG	Trial Management Group
TSC	Trial Steering Committee

WPAI-OA	Work Productivity and Activity Impairment Questionnaire for Osteoarthritis
WOMAC	Western Ontario and McMaster Universities Osteoarthritis Index

## TRIAL SUMMARY

Study Title:	BEhaviour change for People with clinically diagnosed Knee Osteoarthritis: A pragmatic trial (BEPKO-3)
Short study title	BEPKO-3
Local Study Reference:	8360
Study Design:	Pragmatic multi-centre, two-arm, randomised, superiority trial with parallel groups (allocated on a 1:1 ratio) with an embedded qualitative evaluation and parallel cost-effectiveness evaluation.
Study Participants:	Adults with knee Osteoarthritis (OA) who are dissatisfied with the outcome of therapeutic exercise for their knee OA.
Planned Number of Sites:	6
Planned Sample Size:	252
Treatment Duration:	7-9 weeks
Follow Up Duration:	12 months
Intervention	Cognitive Muscular Therapy for knee osteoarthritis. A seven-week individual physiotherapy intervention which incorporates electromyography biofeedback.
Control	Usual NHS care for knee osteoarthritis
Planned Recruitment Start Date:	1 st November 2025
Planned Recruitment End Date:	31 st August 2027
Planned Trial End Date: (final outcomes collected)	31 st June 2028
Planned Study Close Date:	30 th September 2028
Research Question:	What is the clinical and cost-effectiveness of Cognitive Muscular Therapy + usual care compared with usual care alone for people with knee osteoarthritis who have received therapeutic exercise but who are dissatisfied with the outcome.

## FUNDING AND SUPPORT IN KIND

FUNDER(S)	FINANCIAL AND NON-FINANCIAL SUPPORT GIVEN
Research for Patient Benefit National Institute for Health and Care Research (NIHR) [name] [contact]	£ 508,138.00

## ROLES & RESPONSIBILITIES

### Sponsor

The Sponsor, University of Salford, take on overall responsibility for appropriate arrangements being in place to set up, run and report the research project. The sponsor is not providing funds for this study but has taken on responsibility for ensuring finances are in place to support the research.

### Funder

The study is funded by the National Institute for Health & Care Research (NIHR). The NIHR will play no part in the running of the trial or in any data collection, interpretation or analysis of the results

### Trial Management Group

The trial management group (TMG) will include of the chief investigator, trial manager, lead physiotherapist, statistician, health economist, qualitative lead, other co-investigators and at least one PPIE member. This group will meet regularly to oversee the day-to-day management of the trial and ensure it is conducted according to the protocol and will operate according to the TMG charter. Any problems with study conduct and participating centres will be raised and addressed during TMG meetings.

### Trial Steering Committee

The Trial Steering Committee (TSC) will oversee and supervise the progress of the trial and ensure that it is being conducted according to the protocol and the applicable regulations. The TSC is an independent body that includes at least three external academic members (including one statistician) and at least one lay member who are not involved with the running of the trial. The chief investigator, trial manager and statistician will attend these meetings but will be there to present updates and respond to queries and will not participant in decision making. The CI and other trial team members will leave the steering committee meeting when the independent members discuss confidential issues (e.g. performance concerns). TSC Meetings will take place remotely, at least every 6 month or more frequently if required. Given the nature of this study, a separate Data Monitoring Committee (DMC) will not be convened and the TSC will also take on the data monitoring role. At the TSC/DMC meetings, the trial manager will present a summary of screening, recruitment, case report form

returns, treatment withdrawals, site monitoring, treatment adherence and adverse events. There will be no presentation of any unblinded outcome data.

[figure not shown]
#### Protocol Contributors

Several protocol contributors have been involved in the development of this protocol, these include the chief investigator, lead physiotherapist, statistician, health economist, trial manager, PPI members. Protocol contributors are responsible for inputting into the design of the study, ensuring that it is designed transparently and efficiently.

## KEY WORDS

knee osteoarthritis; physiotherapy; rehabilitation; electromyography; biofeedback; behavioural intervention

## TRIAL FLOW CHART

**Definitions:**

MSK CATS = Musculoskeletal Assessment and Treatment Service

GP = General Practitioner

WOMAC = Western Ontario and McMaster Universities Osteoarthritis Index

GAKS = Global assessment of knee symptoms

PCS = Pain Catastrophizing Scale

PSEQ = Pain Self-Efficacy Questionnaire

EQ-5D-5L = EuroQol 5-Dimension 5-Level Questionnaire

WPAI-OA = Work Productivity and Activity Impairment Questionnaire: Osteoarthritis of the Knee

## 1 BACKGROUND

Knee osteoarthritis (OA) is a long-term condition which results in pain, disability and reduced quality of life [1]. One in three people over 40 will develop knee pain within 12 years [2] and 10% of the UK population over the age of 55 will be diagnosed with knee OA [3]. The NICE-recommended clinical pathway for people with knee OA is an initial course of therapeutic exercise [4], delivered either by a physiotherapist or exercise practitioner. If this fails, many of those affected proceed to orthopaedic referral for more invasive treatments, including total knee replacement. Over 115,000 knee replacements are carried out annually in the UK at a cost of over £500 million [5]. Such numbers, and associated healthcare costs, demonstrate that muscle strengthening does not provide sufficient symptom relief for many people with knee OA. Therefore, there is an urgent need to improve the conservative management of people with knee OA who do not respond to therapeutic exercise.

While current guidelines focus on the use of exercises to improve strength, there is clear evidence that people with knee OA over activate their muscles during functional tasks [6-8]. This overactivity is characterised by both increased amplitude [9] and prolonged duration [7] of the contraction of the knee flexor and extensor muscles. Biomechanical research has demonstrated the potentially damaging effects of these patterns, showing that muscle overaction is linked to pain [10], elevated joint load [11] and a more rapid rate of cartilage loss [12]. It is therefore important to understand the potential of conservative management techniques which focus on reducing muscle overactivity.

Psychosocial factors have been linked with clinical pain/disability in knee OA. For example, catastrophising [13] and anxiety [14] have been associated with pain intensity and kinesiophobia linked to physical function [15]. Given these links, physiotherapy interventions have been developed which integrate psychological techniques [16, 17] with muscle retraining. However, these interventions have focused primarily on muscle strength training. Therefore, it is unclear whether improved clinical outcomes would be obtained if psychological techniques were integrated with training to reduce muscle overactivity.

## 2 RATIONALE

Through two research projects (funded by the NIHR) awards we have created, and feasibility tested, a new physiotherapist-led intervention for knee OA [18], called 'Cognitive Muscular Therapy (CMT)'. CMT is an integrated behavioural intervention which integrates psychological techniques for pain management with biofeedback training to reduce muscle overactivity. CMT is delivered through five sequential components, which guide people through a learning journey. As they progress through the treatment, existing illness beliefs are challenged, individuals form a new conceptual model for their condition and learn to change habitual responses to pain. They also learn to consciously reduce overactivity of the knee muscles in standing and during functional tasks.

Our feasibility data demonstrate that the CMT intervention is acceptable to both people with knee OA and physiotherapists and suggest it may deliver medium/large improvements in pain in comparison to usual care. However, in comparison to exercise, which can be delivered in a group setting, the CMT intervention is more resource intensive, requiring seven individual physiotherapist sessions. We therefore propose that CMT should be offered on the NHS if patients with knee OA have tried, but are dissatisfied with, therapeutic exercise. By positioning CMT as second-line treatment, after exercise but before costly orthopaedic referral, we anticipate

more appetite for CMT to be adopted into NHS care pathways. This study has therefore been designed to compare CMT + usual care with usual care alone for people with knee OA who have received therapeutic exercise but who are dissatisfied with the outcome.

## 3 OBJECTIVES AND OUTCOME MEASURES/ENDPOINTS

### 3.1 Aims

The primary aim is to assess whether Cognitive Muscular Therapy (CMT) + usual care results in less knee pain and disability at 1-year post-randomisation compared to usual care alone. We hypothesise that CMT + usual care will be associated with lower composite WOMAC scores at 1 year in comparison to usual care alone for people with a clinical diagnosis of knee OA (OA), who are dissatisfied with the outcome of therapeutic exercise.

Secondary aims include:

- Estimates of treatment effects across a range of secondary outcomes including knee pain, knee function, knee stiffness, pain catastrophizing, pain self-efficacy, global assessment of knee symptoms, quality of life, the impact of knee OA on capacity to work, healthcare use (including knee replacement surgery) and adverse events up to 12-months.
- Within-trial cost utility analysis from an NHS and PSS perspective.
- Qualitative exploration of participants and physiotherapists' experiences and perception of the CMT intervention, beliefs around implementation and involvement in the trial.

### 3.2 Primary Outcome

The primary outcome will be the WOMAC (Western Ontario and McMaster Universities OA Index) composite score [19] at 12 months from randomisation. WOMAC v 3.1 will be used which is composed of three subscales: pain (5 questions), physical function (17 questions) and stiffness (2 questions). Each item is rated on a scale of 0 to 4 (with higher scores indicating worse pain, function, and stiffness), giving a total score ranging from 0 to 96 capturing pain/functional limitation/stiffness from both knees. This outcome is routinely used in large-scale clinical trials of knee OA [20-23] and will therefore facilitate comparison with other clinical trials in this population.

### 3.3 Secondary Outcome measures and endpoints

- Composite WOMAC score [19] at 6-months post-randomisation
- WOMAC pain subscale [19] at 6- and 12-months post-randomisation
- WOMAC function subscale [19] at 6- and 12-months post-randomisation
- WOMAC stiffness subscale [19] at 6- and 12-months post-randomisation
- Global assessment of knee symptoms (GAKS) at 6- and 12-months post-randomisation [24]

- Pain catastrophizing scale (PCS) [25] at 6- and 12-months post-randomisation
- Pain self-efficacy questionnaire (PSEQ) [26] at 6- and 12-months post-randomisation
- Impact of knee OA on capacity to work will be measured with the Work Productivity and Activity Impairment Questionnaire (WPAI-OA) [27] at 6- and 12-months post-randomisation.
- Health-related quality of life will be measured using the EQ-5D-5L at 6- and 12-months post-randomisation. The EQ-5D-5L [28] is a validated measure of health-related quality of life in terms of 5 dimensions (mobility, ability to self-care, ability to undertake usual activities, pain and discomfort, anxiety and depression) each with 5 levels of severity.
- Healthcare resource use at 6- and 12-months will be measured via a custom questionnaire, based on the Client Services Receipt Inventory. Included within this questionnaire will be additional physiotherapy (above that provided to the CMT arm), GP appointments, corticosteroid injections, surgery, imaging, hospital stays and medication use.
- All-cause mortality.
- Adverse events attributable to the trial.
- Serious adverse events.

Our choice of outcomes includes instruments to capture pain, stiffness, activity limitation, psychological factors, global assessment of knee symptoms, quality of life, healthcare resource utilisation and adverse events, including mortality. This outcome set is sufficiently broad to include all components of a core outcome set recommended by OMERACT-OARSI (Outcome Measures in Rheumatology-Osteoarthritis Research Society International) for clinical trials in knee osteoarthritis [24].

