## 9 ADVERSE EVENT MANAGEMENT

### 9.1 Definitions

#### 9.1.1 Adverse Events (AE)

An Adverse Event (AE) is defined as any untoward medical occurrence involving a participant, which does not necessarily have a causal relationship with the intervention or study.

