##### AEs exempt from formal recording

For the intervention group, common AEs listed below that are identified during or after intervention sessions will be recorded on the treatment log (not an AE form), for clinical purposes only:

- Any accidents (e.g. falls) which occur during normal daily activities
- Exacerbation of pre-existing musculoskeletal conditions (including knee pain) which last no more than five days

Any AEs that are not listed above should be recorded using the AE form (See 'Adverse events form'). Forms should be completed by the treating physiotherapist as soon as possible after becoming aware of the AE and sent to the study team. All AEs should be assessed within 24 hours of identification to check if they constitute a 'Serious Adverse Event' as per section 9.1.2 below. If assessed as a Serious Adverse Event, it should be reported within 24 hours, following the procedures outlined in section 9.2.4.

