### 9.2.2 Recording and assessing AEs/SAEs

Participants in the intervention group will be asked about any potential AEs at the start of each face-to-face physiotherapy session. In addition, during the session the treating physiotherapist will monitor for any indications of an AE. Potentially AEs will be evaluated by the treating physiotherapist with follow-up contact from the research team to confirm the details. Participants in the intervention group will also be provided with contact details (generic email address and phone number) for the study team. Whilst participants will not be actively encouraged to report AEs via this route, they may seek advice and help from the study team which may result in AEs being disclosed/discussed. Any AEs, with the exception of those listed in Section 9.1.1, will be recorded on the AE form and stored on the secure trial database unless they fulfil the criteria for a 'Serious Adverse Event' in which case they will be reported to the sponsor via the SAE form (see Section 9.2.3 below).

All AEs should be assessed by an appropriately qualified member of the study team within 72 hours of identification to determine if they meet the criteria to be reported as SAEs as defined in Section 9.1.2. If any AEs meet these criteria, they must be reported to the sponsor within a further 24 hours. If the follow-up questionnaire received from a participant indicates events that may fulfil an SAE, then they should be contacted for further information and an SAE form completed if applicable.

All SAEs should be reported to study team (using the document 'Serious Adverse Event Form'), irrespective of their relationship to the intervention unless they are exempt from reporting (see Section 9.1.2). Once received, the study team review the SAE and request further information if required from the treating physiotherapist or participant appropriate.

The causality of SAEs (i.e. relationship to study intervention) will be assessed by the chief investigator and another appropriately delegated member of the trial team using the classifications in Table 5 below.

Table 3: SAE Causal relationships

Relationship to study intervention	Description
Unrelated	There is no evidence of any causal relationship.

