### 9.2.4 Reporting SAEs

The trial team will liaise with the treating physiotherapist/participant to compile all the necessary information. Once the SAE form has been completed, causality assessments will take place as per section 9.2.2 above. SAEs that are deemed possibly, probably or definitely related to the trial intervention by causality assessor will be notified to the REC within 15 days.

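### Attributable adverse events are a secondary outcome, but the protocol provides a causality assessment only for serious events

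*Protocol*

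**What the plan says.** Protocol section 3.3 has two separate entries among its safety outcomes: "Adverse events attributable to the trial" and "Serious adverse events". Section 9.1.1 defines an AE as "any untoward medical occurrence involving a participant, which does not necessarily have a causal relationship with the intervention or study".

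Section 9.2.2 describes what happens to AEs in the CMT arm. The treating physiotherapist asks about them at the start of each session and evaluates them, and the research team follows up to confirm the details. All AEs are then assessed "within 72 hours of identification to determine if they meet the criteria to be reported as SAEs". Section 9.1.1 asks for the same seriousness check. Non-serious events, apart from those exempted in section 9.1.1, go on the AE form and into the trial database.

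On causality, section 9.2.2 says "The causality of SAEs (i.e. relationship to study intervention) will be assessed by the chief investigator" together with another delegated member of the trial team. The scale is headed "Table 3: SAE Causal relationships". Section 9.2.4 sets the timing: "Once the SAE form has been completed, causality assessments will take place as per section 9.2.2 above". It also sets a cut-off, since SAEs rated possibly, probably or definitely related are notified to the ethics committee.

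**The concern.** An outcome defined by attribution needs someone to judge each event's relationship to the trial. Because the AE definition is neutral on cause, recording an AE does not make it attributable. Because SAEs have their own entry in section 3.3, what the attributable-AE outcome adds is the non-serious events, and those are the events for which section 9 states no relatedness judgement.

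The harms the protocol itself anticipates fall in that gap. The risk assessment in section 6.2 names allergic skin reaction to the EMG sensors and dizziness from the breathing exercises, both of which would ordinarily be non-serious. If ratings are not made when events are confirmed, any later attribution loses contemporaneous detail, may be made with the trial results known, and follows no stated rule. A statistical analysis plan can tabulate ratings but cannot create ones that were not collected.

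**Working it through.** The protocol gives no figure to reproduce. The check sets the steps in section 9 side by side for the two kinds of event.

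| Step | SAE | Non-serious AE on an AE form |
|---|---|---|
| Seriousness check | Yes (9.1.1, 9.2.2) | Yes (9.1.1, 9.2.2) |
| Where recorded | SAE form (9.2.2) | AE form and trial database (9.2.2) |
| Causality assessors | Chief investigator and a delegated team member (9.2.2) | None stated |
| Causality scale | Five levels, Table 3 | None stated |
| When causality is judged | After the SAE form is completed (9.2.4) | None stated |
| Cut-off for related | Possible, probable or definite (9.2.4) | None stated |

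The other mentions of causality do not fill the right-hand column. Section 9.2.3 concerns expected SAEs, and Table 4 in section 9.3 is a table of SAE responsibilities. The physiotherapist's evaluation in section 9.2.2 is the only other assessment of non-serious AEs, and its content is not specified.

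It follows that:
1. Related SAEs can be counted from the Table 3 ratings.
2. Non-serious AEs can be listed and described by type, but the protocol gives no basis for sorting them into attributable and not attributable.
3. The outcome is therefore available in part. The missing part is what distinguishes it from the SAE outcome.

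The scale can only be bounded:
- **Enquiries.** Section 10.1 plans 126 participants per arm and section 6.2 plans 7 sessions, so there are at most 126 × 7 = 882 AE enquiries in the CMT arm. The first enquiry precedes any CMT, which leaves at most 126 × 6 = 756 after exposure. These are ceilings on enquiries, not forecasts of events.
- **Events.** Section 6.2 reports over 200 earlier participants with no adverse events. Assume that those deliveries are comparable and that AEs were ascertained in the same way. The approximate 95% upper bound is then 3/200 = 1.5% of participants, or 126 × 0.015 = 1.9, about 2 people. If ascertainment was looser before, the number could be higher. The protocol gives no figure with which to judge that.

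**The case against.** The strongest reply is that the AE form is a separate document that is not shown and may already hold a relatedness field. That stands as a limit: the protocol does not provide for the judgement, but one cannot say that it will never be made. Even with such a field, the protocol names no assessor, scale or cut-off for non-serious events.

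A second reply is that the two harms named in section 6.2 are described by their cause, and that the physiotherapist evaluates each potential AE. Both are true, but neither amounts to a recorded rating against a stated scale.

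A reader might go further than the documents allow in four ways:
- **That the outcome cannot be produced at all.** Related SAEs can be counted.
- **That the harms profile of CMT would rest on serious events alone.** Non-serious AEs outside the section 9.1.1 exemptions are recorded and can be reported descriptively.
- **That the protocol expects no SAEs.** Section 9.2.3 says only that no expected SAEs have been documented for this intervention before.
- **That late attribution would be biased by knowledge of the arm.** Section 9.2.1 collects non-serious AEs in the CMT arm only, so any assessor knows the arm whenever the rating is made. Only the loss of detail and possible knowledge of results distinguish late from prompt rating.

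It is also fair to say that no efficacy or economic analysis uses AE attribution, and that section 10.5 does not list AEs among the outcomes to be analysed. That limits the weight of the point, but section 3.3 still commits the trial to the outcome.

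**Conclusion.** The concern holds in a limited form. The causality rule in section 9 does not deliver the outcome listed in section 3.3. As written, that outcome yields related SAEs only, and every non-serious event on an AE form is left without a protocol-defined rating. This is a mismatch between two parts of the protocol rather than detail deferred to an analysis plan, because it decides what is collected.

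The practical size is uncertain and may be small, perhaps a handful of events if earlier experience carries over. The primary result is unaffected. The conclusion rests on the protocol text alone and assumes that the unseen AE form does not supply the assessor, scale and cut-off. The mismatch should be corrected before events accumulate unrated.

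**What to change.** In section 9.2.2, have the same assessors apply the Table 3 classification to every event recorded on an AE form, at the time the event is confirmed, and retitle Table 3 to cover AEs and SAEs. In section 3.3, define attributable as a possible, probable or definite relationship to the study intervention, which is the cut already used in section 9.2.4. That also settles the difference between the trial, as worded in section 3.3, and the study intervention, as rated in Table 3.

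Report non-serious attributable AEs as a descriptive rate in the CMT arm, with no between-arm comparison. State that the events exempted in section 9.1.1 are not included. Those are accidents in daily life and musculoskeletal exacerbations lasting no more than five days, and some of the latter could plausibly be related to treatment.

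The alternative is to reword the outcome in section 3.3 to match what is assessed, that is, related SAEs plus a description of recorded non-serious AEs.

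Extending the rating costs one field on the AE form, if it is not already there, and a little assessor time per event. Rewording costs only text, but gives up a count of attributable non-serious harms.

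Two slips can be reconciled in the same edit. Section 9.2.2 points to a Table 5 where Table 3 follows, and the time limit for the seriousness check is 24 hours in section 9.1.1 but 72 hours in section 9.2.2.
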